12.6.1.2 Confirmatory Analysis

The hypothesis to be tested for each of the primary BoExp is that the geometric mean level on Day 5 of the BoExp for THS 2.2 is lower relative to CC.

Analysis of the primary BoExp will be conducted on the natural log scale. In order to test the follow hypothesis

$$\text{Null hypothesis (H}_0\text{): } m_1 \geq m_2$$

Alternative hypothesis (H_1): $m_1 < m_2$

Where m_1 and m_2 are the geometric means of the BoExp levels on Day 5 for THS 2.2 and CC respectively.

The SAS code will be the same as described in Section 12.6.1.1 “Primary Biomarkers of Exposure in 24 hour collection”.

The confirmatory analysis will be performed on the FAS only. However, if the PP and FAS differ by more than 10 subjects then the analysis will be repeated for the PP population.

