12.1.5 Significance Level for Inferential Analysis

Unless stated otherwise, all statistical tests will be two-sided and conducted at the 5% level, and all quoted confidence intervals (CIs) will be two-sided 95% CIs.

The primary endpoints will be tested using a multiple testing procedure to preserve the overall alpha level by simultaneously testing the endpoints using a closed procedure with each test performed at an alpha level of 5%. This implies that statistical significance is required for all primary endpoints in order to be able to make confirmatory claims about any of the endpoints.

Full details of this approach will be provided in the SAP.

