12.4 Primary Analysis

12.4.1 Primary Endpoint Analysis Variables

The primary endpoints are:

- COHb on Day 5.
- MHBMA on Day 5.

Confidentiality statement: Data and information contained in this document are considered to constitute trade secrets and confidential commercial information, and the legal protections provided to such trade secrets and confidential information are hereby claimed under the provisions of applicable law. No part of this document may be publicly disclosed without the written consent of Philip Morris Products S.A.

- 3-HPMA on Day 5.
- S-PMA on Day 5.

See section 3.4.1.

Evaluation Criterion: The study will be considered successful if the study demonstrates a 50% reduction or more for all four primary BoExp in the THS 2.2 arm compared to the CC arm (as measured on Day 5), using a one-sided test with 2.5% type I error probability.

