12.4.4 Confirmatory Analysis

The hypothesis to be tested for each of the primary and secondary biomarkers of exposure is that the geometric mean level on Day 5 of the biomarker for THS 2.2 is lower relative to CC.

Analysis of BoExp will be conducted on the natural log scale. In order to test the following hypothesis

Null hypothesis (H0): $m_1 \geq m_2$

Alternative hypothesis (H1): $m_1 < m_2$

Where m_1 and m_2 are the geometric means of the biomarker levels on Day 5 for THS 2.2 and CC respectively.

The transformed data will be analyzed by means of a generalized linear model using product arm as covariate adjusting for the following baseline information: sex, average cigarette

consumption over the previous 4 weeks, and baseline value of endpoint. Estimates of differences between groups will be back-transformed to provide relative effects.

Assumptions of the analysis of variance model will be tested. Markedly non-lognormally distributed BoExp data will be transformed or analyzed by appropriate non-parametric methods.

Should more than 20% of the subjects be excluded from the FAS, would the above confirmatory analysis will be repeated on the PP population.

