5.5 Study Hypotheses And Evaluation Criteria

5.5.1 Hypotheses

The hypothesis to be tested for each of the primary and secondary BoExp is that the geometric mean level on Day 5 of the BoExp for THS 2.2 is lower relative to CC.

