5.5.2 Evaluation Criteria

The study will be considered successful if the study demonstrates a 50% or more reduction in MHBMA, 3-HPMA, S-PMA, and COHb in the THS 2.2 arm compared to the CC arm (as measured on Day 5), using a one-sided test with 2.5% type I error probability.

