**Table 13: Expected Power (YVD-CS01-EU and ZRHX-EX-01 Studies Assumptions)**

Assumptions	Reduction					
	50%	51%	52%	53%	54%	55%
YVD-CS01-EU	96%	91%	85%	75%	63%	48%
ZRHX-EX-01	>99%	>99%	96%	81%	48%	16%

A total of 160 smokers (80 in THS 2.2, 40 in CC, and 40 in the SA arm) will be randomized to demonstrate a reduction of at least 50% on 4 primary BoExp in smokers switching from CC to THS 2.2 as compared to those continuing to smoke CC, using one-sided test with 2.5% type I error probability.

The sample size is sufficient to obtain 95% CIs for the ratio between (geometrical) mean levels of primary BoExp in THS 2.2 and SA with upper and lower limits deviating not more than 18% from the point estimates, with an 80% overall probability of achieving the desired precision of estimating the true mean.

This study has 80% power using a one-sided test with 2.5% type I error probability:

- To detect a 0.631 [mL/min/kg] (29%) difference between THS 2.2 and CC in CYP1A2 activity, as measured by the CAF clearance, assuming a standard deviation (SD) of 0.564. Effect size and variability are derived from data obtained in the YVD-CS01-EU study sponsored by PMI.
- To detect a 24.71 [ng/g creatinine] (20%) difference between THS 2.2 and CC in 11-DTX-B2, assuming a SD of 43.78. The anticipated effect size of THS 2.2 is assumed to be about 90% of the effect of smoking cessation.

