12.6.1 Primary Analyses

12.6.1.1 Primary Biomarkers of Exposure in 24 hour collection

The primary BoExp (COHb in blood and urinary concentrations adjusted for creatinine of MHBMA, 3-HPMA and S-PMA) will be summarized as detailed in Section 12.1.3 “Descriptive Statistics”.

The baseline is as defined in Section 12.1.4 “Definitions for Statistical Data Analysis”,

The values and percent changes in the concentration adjusted for creatinine will be listed and summarized along with the COHb concentrations and percent changes from baseline. In addition line graphs will be produced for means (and 95% CI) over all timepoints.

For all arms the 24 hour urine collection will be collected daily from Day -1 to Day 5. Although the 24 hour urine collection will span into the following Day it will be reported by the day the collection started.

The primary endpoints will be log-transformed (base_e) prior to analysis. The analysis will compare (1) last Day 5 values of COHb in blood and (2) urinary concentrations of MHBMA, 3-HPMA and S-PMA corrected for creatinine on Day 5 between the THS 2.2 and CC arms. An ANCOVA (Snedecor and Cochran 1982) model will be used with terms for the log-transformed baseline value, sex, average daily CC consumption over the last 4 weeks as reported during screening and product.

The SAS code to be used is shown below:

```
Proc mixed data=_data_ ;
Class product sex cigarette_cons ;
Model log (Day 5) = log (baseline) sex cigarette_cons product ;
Lsmean product / pdiff =control('CC') alpha=0.05 cl ;
Run ;
```

The least squares (LS) means and estimate of the difference along with it's 95% CI will be back-transformed before presenting in the tables. The geometric LS means for each product along with the ratio (THS 2.2 : CC) and 95% CI will be presented in the tables.

In addition line graphs will be produced for product means (and 95% CI) over all timepoints for COHb in blood and urinary concentrations adjusted for creatinine of MHBMA, 3-HPMA and S-PMA.

The data will be presented in the below outputs, the TFL number refers to the TFL number in the accompanying TFL shell document:

TFL number	Title
FIGURES	
15.1.1.1	Blood COHb (%) Mean and 95% CI– FAS
15.1.1.2	MHBMA Urinary Concentration Adjusted for Creatinine (units) Mean and 95% CI – FAS
15.1.1.3	3-HPMA Urinary Concentration Adjusted for Creatinine (units) Mean and 95% CI– FAS
15.1.1.4	S-PMA Urinary Concentration Adjusted for Creatinine (units) Mean and 95% CI– FAS

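### The confirmatory hypothesis for the primary biomarkers tests for any reduction, while study success requires a demonstrated reduction of at least 50%

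*SAP*

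**What the plan says.** **Hypothesis.** SAP 12.6.1.2 (Confirmatory Analysis) states for each primary biomarker that "the geometric mean level on Day 5 of the BoExp for THS 2.2 is lower relative to CC", and sets H0: m1 ≥ m2 against H1: m1 < m2, where m1 and m2 are the Day 5 geometric means for THS 2.2 and CC. Protocol 12.4.4 gives the same pair of hypotheses, in the words "the geometric mean level on Day 5 of the biomarker for THS 2.2 is lower relative to CC". SAP 5.5.1 uses one statement for primary and secondary biomarkers alike: "The hypothesis to be tested for each of the primary and secondary BoExp is that the geometric mean level on Day 5" is lower for THS 2.2. None of these carries a margin.

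**Success criterion.** SAP 5.5.2: "The study will be considered successful if the study demonstrates a 50% or more reduction in MHBMA, 3-HPMA, S-PMA, and COHb". The comparison is THS 2.2 against CC on Day 5. Protocol 12.4.1 has the same threshold for all four biomarkers, "using a one-sided test with 2.5% type I error probability"; SAP 5.5.2 also attaches that test.

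**Analysis and output.** SAP 12.6.1.1 fits an ANCOVA on the log scale and contrasts the product LS means with CC. The code has no shifted null. The planned output is: "The geometric LS means for each product along with the ratio (THS 2.2 : CC) and 95% CI will be presented".

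**Sample size.** SAP Section 8 randomizes 160 smokers "to demonstrate a reduction of at least 50% on 4 primary BoExp in smokers switching from CC to THS 2.2".

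**Multiplicity and level.** SAP 12.1.7 requires significance on all four primary endpoints before any confirmatory claim, each test at 5%. The default in Protocol 12.1.5 is that "all statistical tests will be two-sided and conducted at the 5% level".

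**The concern.** The section that defines the confirmatory test and the section that defines success concern the same four endpoints but different null hypotheses. A test of m1 < m2 cannot demonstrate halving, however small its p-value. SAP 12.1.7 rests confirmatory claims on statistical significance, and the only hypotheses written for that significance have their boundary at a ratio of 1.

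This leaves the primary claim open to more than one reading after the data are seen:

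- significance against a ratio of 1;
- significance against a ratio of 1 plus a point estimate at or below 0.50;
- an upper confidence limit below 0.50.

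COHb is where the readings are most likely to diverge, because its expected ratios (0.40 and 0.44 in SAP Tables 11 and 12) lie closest to 0.50. At YVD variability, an observed COHb ratio between 0.44 and 0.50 passes the second reading and fails the third.

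**Working it through.** **Inputs.** Arms of 80 (THS 2.2) and 40 (CC), one-sided 2.5% (SAP Section 8). Mean ratio (CV) from SAP Table 11, YVD-CS01-EU: COHb 0.40 (0.32), 3-HPMA 0.30 (0.50), MHBMA 0.15 (0.70), S-PMA 0.20 (0.70). From SAP Table 12, ZRHX-EX-01: 0.44 (0.14), 0.28 (0.20), 0.11 (0.47), 0.07 (0.50).

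**Formulas.** Log-scale SD = √ln(1 + CV²). SE = SD × √(1/80 + 1/40) = SD × 0.1936. Per-endpoint rejection probability comes from the noncentral t with 118 df and noncentrality ln(true ratio / null ratio)/SE. Joint values are products over the four endpoints, so independence is assumed. The YVD SEs are 0.0605 (COHb), 0.0915 (3-HPMA) and 0.1223 (MHBMA and S-PMA).

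**Step 1: which null does the plan's power table use?** Set the null ratio to 1 minus the reduction in each column of SAP Table 13 (Protocol Table 18), YVD row:

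| Reduction | 50% | 51% | 52% | 53% | 54% | 55% |
|---|---|---|---|---|---|---|
| Null ratio | 0.50 | 0.49 | 0.48 | 0.47 | 0.46 | 0.45 |
| Recomputed joint power | 95.5% | 91.4% | 84.8% | 75.2% | 62.8% | 48.5% |
| Printed | 96% | 91% | 85% | 75% | 63% | 48% |

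With the null at 1, joint power is about 100% under both sets of assumptions, which does not match the table. So the study was sized for a null at the margin.

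In the ZRHX row the 50% column agrees (99.7%; printed >99%). The columns from 51% to 55% recompute to 97.7, 89.2, 67.9, 37.2 and 12.8%, against printed >99, 96, 81, 48 and 16%. That row is therefore not fully reproduced from the printed COHb CV of 0.14; a CV near 0.12 comes close. This does not change which null was used.

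**Step 2: largest observed ratio that is significant.** Cut-off = null × exp(−1.980 × SE), YVD CVs:

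| | Written null (1) | Null at 0.50 |
|---|---|---|
| COHb | exp(−0.1198) = 0.89 | 0.44 |
| 3-HPMA | exp(−0.1812) = 0.83 | 0.42 |
| MHBMA, S-PMA | exp(−0.2422) = 0.78 | 0.39 |

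Observed ratios between the two columns reject the written null without demonstrating a 50% reduction.

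**Step 3: how often the written nulls are rejected when the criterion is not met.** YVD CVs, same true ratio for all four:

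| True ratio | COHb | 3-HPMA | MHBMA | S-PMA | All four |
|---|---|---|---|---|---|
| 0.60 | >99.9% | 99.98% | 98.6% | 98.6% | 97% |
| 0.70 | 99.99% | 97.2% | 82.5% | 82.5% | 66% |
| 0.80 | 95.5% | 67.7% | 44.0% | 44.0% | 13% |

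With ZRHX CVs the last column is >99.9%, 96% and 49%.

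If only COHb falls short and the other three sit at their YVD planned ratios, all four written nulls are rejected with probability >99.9% at a true COHb ratio of 0.60 or 0.70, and 95.5% at 0.80. With the null at 0.50, COHb alone passes 2.5% of the time at a true ratio of 0.50 and 0.02% at 0.55.

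**The case against.** The strongest reply is that a success rule already exists. Protocol 12.4.1 and SAP 5.5.2 state the margin, the four endpoints, the requirement that all four succeed, the sidedness and the alpha. The natural reading is a one-sided 2.5% test at 0.50, which is equivalent to the upper limit of the two-sided 95% CI lying below 0.50, and SAP 12.6.1.1 already plans that interval. Nothing equates rejecting m1 ≥ m2 with success, and the hypothesis may be a generic one shared with the secondary biomarkers, which have no threshold. The rejection probabilities in Step 3 are then not false-success rates. They also apply at true ratios well above the planned 0.07 to 0.44; at the planned values either rule passes with high probability.

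Much of this stands. The intended rule can be inferred, and the 50% criterion does not lack a test. It is also true that SAP 12.6.1.1 lists the ratio and CI rather than a p-value for the tables, and that the separate table shells, which the SAP mentions, were not available.

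It does not remove the contradiction. The section headed Confirmatory Analysis specifies a different test for these four endpoints, SAP 12.1.7 ties confirmatory claims to significance, and SAP Section 9 does not address the point. A reader has to choose between two written statements, and the choice decides the primary conclusion over a wide range of results.

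**Conclusion.** The concern holds. The written confirmatory null (ratio 1) is the wrong test for the stated success criterion (ratio 0.50), in both the protocol and the SAP, and nothing in either document links the planned CI to 0.50. At YVD variability the two statements disagree for any observed COHb ratio from about 0.44 to 0.89. With all four true ratios at 0.60, a 40% reduction, the written nulls would all be rejected about 97% of the time although the criterion is not met.

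These figures rest on 80 vs 40 evaluable subjects, the CVs in SAP Tables 11 and 12, a two-sample comparison without covariate adjustment, and, for joint values, independence of the four biomarkers. Positive dependence would raise the joint probabilities: the 13% at a true ratio of 0.80 could reach 44%, the lowest single-endpoint value. The contradiction itself does not depend on any of these assumptions. Because it concerns the decision rule for the primary claim, it should be corrected before unblinding.

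**What to change.** 1. In Protocol 12.4.4 and SAP 5.5.1 and 12.6.1.2, for the four primary biomarkers, state H0: m1/m2 ≥ 0.50 against H1: m1/m2 < 0.50 at one-sided 2.5%.
2. Add the decision rule: success is declared only if the upper limit of the two-sided 95% CI of the THS 2.2:CC geometric LS mean ratio is below 0.50 for all four.
3. Keep H0: m1 ≥ m2 for the secondary biomarkers, stated separately.
4. If the protocol is not amended, record the change in SAP Section 9.
5. As a minor clarification, say in SAP 12.1.7 that the 5% is two-sided, that is, one-sided 2.5%.

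The cost is wording, plus comparing an already planned confidence limit with 0.50. Data, model and sample size do not change, and the stated power in the 50% column (96% and >99%) already refers to this null.

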12.6.2 Secondary Analyses

12.6.2.1 Biomarkers of Exposure

In addition, the quantity excreted over 24 hours for MHBMA, 3-HPMA and S-PMA will be presented.

The PP Population will be used to examine the robustness of the analysis of the primary endpoints. The primary analysis on the FAS will be repeated on the PP population using the same methodology as detailed in Section 12.6.1.1 “Primary Biomarkers of Exposure in 24 hour collection”.

The primary BoExp will also be examined to compare the reductions in THS 2.2 vs. SA using the same methodology as for the primary analysis.

The secondary BoExp are exhaled CO, total 1-OHP in urine, Total NNN in urine, 4-ABP in urine, 1-NA in urine, 2-NA in urine, o-tol in urine, CEMA in urine, HEMA in urine, B[a]P in urine, HMPMA in urine, S-BMA in urine, Total NNAL in urine and NEQ in urine. The urine parameters will be expressed as concentrations adjusted for creatinine and the quantity excreted over 24 hours.

The baseline of the exhaled CO will be the time-matched measurements on Day 0, i.e. the 1st measurement on Days 1 to 5 will be matched to the 1st measurement on Day 0 and similarly for the 2nd, 3rd and 4th measurements. The baseline of the urinary biomarkers will be the last assessment prior to 06:29 AM on Day 1.

The values and percent changes for urinary BoExp in the quantity excreted over 24-hours and the concentration adjusted for creatinine will be listed and summarized. In addition line graphs will be produced for product means (and 95% CI) over all timepoints.

CO in exhaled breath will be measured using the Micro+™ Smokerlyzer® or similar device, conducted on Day -2 to Day 6. On Day -1 to Day 5 the first test per day will be performed within 15 minutes prior to the first product use and then between 12:00 and 01:30 PM, between 04:00 and 05:30 PM and between 08:00 and 09:30 PM. On Days -2 and Day 6 the CO breath tests will be conducted once.

Descriptive statistics summarized by exposure will be produced separately for all timepoints for all visits applicable for exhaled CO. This will be done on the FAS, stratified by sex, and CC consumption.

Actual values and percent changes from baseline in levels of exhaled CO will be listed and summarized. In addition line graphs will be produced for product means (and 95% CI) over all timepoints.

The last measurement of exhaled CO will be used in the analysis. An ANCOVA model will be used with terms for the baseline value, sex, average daily CC consumption over the last 4 weeks as reported during screening and product. No adjustment will be made for multiple comparisons.

The analysis will compare the log-transformed urinary concentrations corrected for creatinine on Day 5 to 6 and the quantity excreted over 24-hours on Day 5 to 6 between the THS 2.2 and CC arms. An ANCOVA model will be used with terms for the log-transformed baseline value, sex, average daily CC consumption over the last 4 weeks as reported during screening and product. No adjustment will be made for multiple comparisons.

The SAS code will be the same as described in Section 12.6.1.1 “**Primary Biomarkers of Exposure in 24 hour collection**”.

LS means for each product along with the difference (THS 2.2 - CC) and 95% confidence interval (CI) will be presented in the tables.

The secondary BoExp will also be examined to compare the reductions in THS 2.2 vs. SA using the same methodology as above.

TFL number	Title
FIGURES	
15.1.2.1	Urinary MHBMA Quantity Excreted Over 24 hours Mean and 95% CI– FAS
15.1.2.2	Urinary 3-HPMA Quantity Excreted Over 24 hours Mean and 95% CI– FAS
15.1.2.3	Urinary S-PMA Quantity Excreted Over 24 hours Mean and 95% CI– FAS
15.1.2.4	Exhaled CO Arithmetic Mean and 95% CI– FAS
15.1.2.5	1-OHP Urinary Concentration Adjusted for Creatinine Mean and 95% CI– FAS
15.1.2.6	Urinary 1-OHP Quantity excreted Over 24 hours Mean and 95% CI– FAS
15.1.2.7	Total NNN Urinary Concentration Adjusted for Creatinine Mean and 95% CI– FAS
15.1.2.8	Urinary Total NNN Quantity Excreted Over 24 hours Mean and 95% CI– FAS

TFL number	Title
15.1.2.9	4-ABP Urinary Concentration Adjusted for Creatinine Mean and 95% CI- FAS
15.1.2.10	Urinary 4-ABP Quantity Excreted Over 24 hours Mean and 95% CI- FAS
15.1.2.11	1-NA Urinary Concentration Adjusted for Creatinine Mean and 95% CI- FAS
15.1.2.12	Urinary 1-NA Quantity Excreted Over 24 hours Mean and 95% CI- FAS
15.1.2.13	2-NA Urinary Concentration Adjusted for Creatinine Mean and 95% CI- FAS
15.1.2.14	Urinary 2-NA Quantity Excreted Over 24 hours Mean and 95% CI- FAS
15.1.2.15	o-tol Urinary Concentration Adjusted for Creatinine Mean and 95% CI- FAS
15.1.2.16	Urinary o-tol Quantity Excreted Over 24 hours Mean and 95% CI- FAS
15.1.2.17	CEMA Urinary Concentration Adjusted for Creatinine Mean and 95% CI- FAS
15.1.2.18	Urinary CEMA Quantity Excreted Over 24 hours Mean and 95% CI- FAS
15.1.2.19	HEMA Urinary Concentration Adjusted for Creatinine Mean and 95% CI- FAS
15.1.2.20	Urinary HEMA Quantity Excreted Over 24 hours Mean and 95% CI- FAS
15.1.2.21	B[a]P Urinary Concentration Adjusted for Creatinine Mean and 95% CI- FAS
15.1.2.22	Urinary B[a]P Quantity Excreted Over 24 hours Mean and 95% CI- FAS
15.1.2.23	3-HMPMA Urinary Concentration Adjusted for Creatinine Mean and 95% CI- FAS
15.1.2.24	Urinary 3-HMPMA Quantity Excreted Over 24 hours Mean and 95% CI- FAS
15.1.2.25	S-BMA Urinary Concentration Adjusted for Creatinine Mean and 95% CI- FAS
15.1.2.26	Urinary S-BMA Quantity Excreted Over 24 hours Mean and 95% CI- FAS
15.1.2.27	Total NNAL Urinary Concentration Adjusted for Creatinine Mean and 95% CI- FAS
15.1.2.28	Urinary Total NNAL Quantity Excreted Over 24 hours Mean and 95% CI- FAS
15.1.2.29	NEQ Urinary Concentration Adjusted for Creatinine Mean and 95% CI- FAS
15.1.2.30	Urinary NEQ Quantity Excreted Over 24 hours Mean and 95% CI- FAS
TABLES	
15.2.4.1	Analysis of Blood COHb (%) versus CC on Day 5 – PP Population
15.2.4.2	Analysis of MHBMA Urinary Concentration Adjusted for Creatinine (units) versus CC on Day 5 – PP Population

TFL number	Title
15.2.4.3	Analysis of 3-HPMA Urinary Concentration Adjusted for Creatinine (units) versus CC on Day 5 – PP Population
15.2.4.4	Analysis of S-PMA Urinary Concentration Adjusted for Creatinine (units) versus CC on Day 5 – PP Population
15.2.4.5	Analysis of Primary Biomarkers of Exposure versus SA on Day 5 – FAS
15.2.4.6	Analysis of Urinary Quantity Excreted of MHBMA, 3-HPMA and S-PMA over 24 hours on Day 5 – FAS
15.2.4.7	Descriptive Statistics of Urinary Quantity Excreted of MHBMA over 24 hours (units) – FAS
15.2.4.8	Descriptive Statistics of Urinary Quantity Excreted of 3-HPMA over 24 hours (units) – FAS
15.2.4.9	Descriptive Statistics of Urinary Quantity Excreted of S-PMA over 24 hours (units) – FAS
15.2.4.10	Analysis of Exhaled CO (ppm) on Day 5 – FAS
15.2.4.11	Descriptive Statistics of Exhaled CO (ppm) – FAS
15.2.4.12	Descriptive Statistics of Time Matched Changes (%) in Exhaled CO – FAS
15.2.4.13	Analysis of Urinary 1-OHP on Day 5 – FAS
15.2.4.14	Descriptive Statistics of Urinary 1-OHP – FAS
15.2.4.15	Analysis of Urinary Total NNN on Day 5 – FAS
15.2.4.16	Descriptive Statistics of Urinary Total NNN – FAS
15.2.4.17	Analysis of Urinary 4-ABP on Day 5 – FAS
15.2.4.18	Descriptive Statistics of Urinary 4-ABP – FAS
15.2.4.19	Analysis of Urinary 1-NA on Day 5 – FAS
15.2.4.20	Descriptive Statistics of Urinary 1-NA – FAS
15.2.4.21	Analysis of Urinary 2-NA on Day 5 – FAS
15.2.4.22	Descriptive Statistics of Urinary 2-NA – FAS
15.2.4.23	Analysis of Urinary o-tol on Day 5 – FAS
15.2.4.24	Descriptive Statistics of Urinary o-tol – FAS
15.2.4.25	Analysis of Urinary CEMA on Day 5 – FAS
15.2.4.26	Descriptive Statistics of Urinary CEMA – FAS
15.2.4.27	Analysis of Urinary HEMA on Day 5 – FAS
15.2.4.28	Descriptive Statistics of Urinary HEMA – FAS
15.2.4.29	Analysis of Urinary B[a]P on Day 5 – FAS
15.2.4.30	Descriptive Statistics of Urinary B[a]P – FAS
15.2.4.31	Analysis of Urinary HMPMA on Day 5 – FAS
15.2.4.32	Descriptive Statistics of Urinary HMPMA – FAS
15.2.4.33	Analysis of Urinary S-BMA on Day 5 – FAS
15.2.4.34	Descriptive Statistics of Urinary S-BMA – FAS
15.2.4.35	Analysis of Urinary Total NNAL on Day 5 – FAS
15.2.4.36	Descriptive Statistics of Urinary Total NNAL – FAS
15.2.4.37	Analysis of Urinary NEQ on Day 5 – FAS
15.2.4.38	Descriptive Statistics of Urinary NEQ – FAS

TFL number Title

LISTINGS

